### **Study Visits:**

Potential participants will complete the following:

- 1) A phone or online screen to determine initial eligibility via UNC's REDCap

- 2) A 1-2 clinical characterization visit(s) to determine eligible, and, if eligible, to characterize participants clinically. During COVID, can be split remote/in-person.
- 3) A pre-treatment 7 Tesla (7T) fMRI scan & if one of the first 60 subjects enrolled, have an initial blood draw of 10ml (2tsp). Update, the NARSAD blood protocol had entered an extension and has additional funds so up to 210 participants, in both phases, will have an initial blood draw of 10ml (2tsp). **As of 6/26/20, the blood protocol will no longer continue for any new participant enrolled in the study. As of the NCE 2022, this current amendment, imaging of new participants will end. Only enrollment into the therapy portion at Duke will continue.**
- 4) Patients will then be assigned randomly to the experimental treatment (BATA) or comparison treatment (Mindfulness Based Cognitive Therapy (MBCT)) for approximately 15 weeks of treatment.
- 5) The first 60 patients enrolled (n=30 who receive BATA and n=30 who receive MBCT) will additionally complete two additional, mid-treatment, fMRI scans as well as an additional blood draw at all other MRI visits. The 1st phase of the study entered the R61 no cost extension at the end of the project period & due to limited funds, participants will no longer be receiving up to 4 scans. Participants who consent at UNC on or after 11/1/18 will receive only pre- and post-treatment scans (2 scans total). **The R61 no cost extension has ended and the study has entered the larger R33 phase of the study and participants will continue to receive only pre and post treatment scans (2 total) and no bloodwork will be collected starting summer 2020 for new participants. \*\*No new enrollment to imaging at UNC will occur with the approval of the June 2022 NCE amendment.**
- 6) A post-treatment clinical characterization visit
- 7) A post-treatment 7T scan

#### 4.2 EFFICACY ASSESSMENTS & STUDY PROCEDURES

##### **Pre-Treatment eligibility and diagnostic assessment and participant characterization (at the Duke CBRTP):**

**This session will be completed by a study coordinator or assessor at Duke who is study personnel on the companion Duke IRB protocol. The following assessments will be conducted over 1-2 visits (some can be completed remotely):**

##### **Eligibility and diagnostic assessment measures:**

**1) The Columbia Suicide Severity Rating Scale (C-SSRS)** will be administered. Participants indicating "yes" on items 4 (Active Suicidal Ideation with Some Intent to Act, without Specific Plan) and/or 5 (Active Suicidal Ideation with Specific Plan and Intent) within the last month will be excused from the trial and referred to more intensive clinical management. The C-SSRS will be used during the initial assessment visit over the past 1 month and then used to assess "since the last study visit" at the in-person assessment visit, if applicable during COVID-19, and the weeks 4, 8, 12 therapy visits that include the computer tasks and the final therapy/post-treatment visit. During the 1-2 remote & in-person assessment screening visits, if the participant has a 4 or 5 on the CSSRS, they will no longer be eligible for the study as per inclusion/exclusion criteria. **COVID-19 Update:\*\*Please note that the conduct of the CSSRS with computer tasks at the inperson assessment visit, wks 4, 8, 12 and final visit and are contingent upon the building availability and approval of in-person visits either at Duke or UNC. If not available and approved, the computer tasks with CSSRS will be omitted until the study team have the appropriate approvals to do the tasks at an in-person visit. These omissions (skipping the inperson visit) will not be considered protocol deviations since the omissions are necessary to be able to open the study and begin to collect the main primary outcomes of imaging and therapy.**

**2)** The SHAPS will be repeated to verify a score of  $\geq 30$ , corresponding to clinically significant anhedonia. **If the SHAPS score is  $<30$ , the participant will be ineligible (R33 phase);**

**3)** Clinician's Global Impression Scale-Severity score (CGI-S) = 3 to assure a clinically impaired sample. If the CGI score is 2 or less, the participant will be ineligible;

**4)** The Structured Clinical Interview for DSM Disorders-5 Research Version (SCID-5-RV) will be administered to assess exclusionary conditions and to characterize the sample. Individuals with primary anhedonia but no DSM diagnosis will be included. Exclusionary axis I disorders include:

- Those for whom medication management is the primary gold-standard treatment, including those with bipolar disorder/mania, schizophrenia spectrum, and other psychotic disorders; (to clarify, if a subject meets criteria for current or lifetime history of bipolar I and II is exclusionary).
- Those who may have difficulty understanding the cognitive components of BATA, including those with intellectual disability, neurocognitive disorders, and dissociative disorders;
- Feeding and eating disorders which may have confounding effects on the BOLD fMRI signal;
- Substance Use Disorders given confounding effects of substances of abuse on the BOLD fMRI signal; At screening if subject reported use of a substance of abuse in the past week, they will be excluded to ensure acute drug effects. Lifetime history of moderate or severe non-alcohol substance use disorder on SCID-5 is also excluded. Lifetime history of severe alcohol use disorder on SCID-5 will be excluded.

**5)** North American Adult Reading Test (NART) will be administered & NART calculated IQ score should be 90 or higher for study eligibility.

Participant characterization:

Next, the assessor will conduct a brief interview examining medical and treatment history using: 1) The 7T MRI Adult Safety Screen (completed as part of prescreening & reviewed by UNC study team at pre scan visit at the BRIC. **Removed in the NCE June 2022 since no longer enrolling to MRI at UNC.**

2) an abbreviated version of the Treatment History Interview (THI) will be used to assess previous and any ongoing psychiatric services received. The modified THI will be administered at the initial assessment visit(s) ONLY. Those who have any contraindications for MRI or report taking psychotropic medications and/or being in psychotherapy currently will not qualify.

3) Urine Drug Screen-Subjects will undergo a urinalysis drug screen and those positive for cocaine, marijuana, opiates, methadone, methamphetamine will be excluded at study entry. ADHD medications (amphetamines) and benzodiazepines will not be excluded from the study if participant is taking them by prescription. (COVID-19: Will be done at the 2nd assessment visit, which is in-person, only after determining clinical assessment eligibility).

Eligible participants will complete the following assessments:

For included participants, the subject will then complete the two computer reward tasks next because fatigue can affect their performance. Thus it is important to complete these tasks as soon as eligibility is confirmed.

- The Effort Expenditure for Rewards Task (EEfRT). The EEfRT is a computer task that takes 20 minutes and indexes the willingness to work for rewards under varying conditions of reward probability and magnitude. On each trial, participants simply select whether they wish to do an easy task (pressing a key 10 times with their dominant index finger) for a relatively smaller reward or a slightly harder task (pressing a key 100 times with their non-dominant finger) for a relatively larger reward.
- The Probabilistic Reward Task (PRT). The PRT is a computer-task that takes 20 minutes that is sensitive to behavioral shifts driven by reward in anhedonic patients. One of two reward-based responses receives feedback more frequently; this asymmetry typically induces bias toward the more frequently rewarded response. (COVID-19: Computers tasks will be done at the 2nd visit, which is in-person with an additional completion of another CSSRS at the end of the tasks, only after determining eligibility). COVID-19

Update:\*\*Please note that the conduct of the computer tasks with additional CSSRS at the in-person assessment visit and the urine drug screen are contingent upon the building availability and approval of in-person visits either at Duke or UNC. If not available and approved, the computer tasks with CSSRS and urine drug screen in person visit will be omitted until the study team have the appropriate approvals to do the tasks at an in-person visit. These omissions will not be considered protocol deviations since the omissions are necessary to be able to open the study and begin to collect the main primary outcomes of imaging and therapy. **NCE June 2022-tasks will only be done at Duke. Enrollment to UNC procedures is ending.**

3) *REDCap Self-report Questionnaires*

- a) Demographic Data Survey (DDS)
- b) PhenX Toolkit Core Tier 1 Impairment measures related to depressed mood
- c) PhenX Toolkit Core Tier 2 measures of perceived stress and life events
- d) The Beck Depression Inventory II (BDI-II)
- e) The Beck Anxiety Inventory (BAI)
- f) The Penn State Worry Questionnaire (PSWQ)
- g) The PTSD Checklist for DSM5 (PCL-5)
- h) Short Form-36 Health Survey, a widely used metric of quality of life
- i) Childhood Trauma Questionnaire (CTQ)
- j) Inventory of Depression & Anxiety Symptoms (IDAS)
- k) Toronto Mindfulness Scale (TMS) to measure trait mindfulness
- l) Social Responsiveness Scale, version 2 (SRS-2) to collect a rating around social deficits in the population which could impact ratings of anhedonia.

**For the R33 phase,** the Inventory of Depression and Anxiety Symptoms [IDAS] and Social Responsiveness Scale, version 2 [SRS-2] is not collected. In addition to the measures listed above, in the R33 phase, we will collect Motivation and Pleasure Scale-Self Report [MAPS] to measure motivation and pleasure domains of negative symptoms, and collect Inventory of Depressive Symptomatology-Self-Report [IDS-SR] anhedonia items and Behavioral Activation for Depression Scale [BADS] to measure change in anhedonia, avoidance and activation. Participants can either complete these in person or be sent the REDCap survey invitation link to complete at the end of the remote or in-person assessment visit.

At the end of the clinical interview/assessment visit(s) all eligible participants will be scheduled for the 7T MRI scan at UNC's BRIC. The MRI will be planned for at least one day later, and up to 2 weeks later. If a subject is unable to be logistically scheduled for an fMRI until between 2-4 weeks past screening, we will still schedule them for an MRI at the UNC BRIC. Anyone going over 4 weeks, will be considered a screen fail and not randomized and have the ability to rescreen at a later date (i.e. will sign another econsent, redo SHAPS, C-SSRS, UA drug screen [if possible during COVID times], all self-report, SCID5, THI and computer tasks [if possible & contingent on ability to have in-person visits]). Their NART will not be redone and can be used for the rescreen. Knowing this, we will aim to schedule participants for their brain scan as soon as possible after their assessment day and also have informed subjects in the online/phone screen. Subjects who are THC smokers (and do not meet criteria for a current THC use disorder & have a negative urine drug screen at intake & confirm no use in the past 1 week) will be reminded to not smoke within 24 hours of the MRI scan visit as well as the future week 4, 8, 12 & post-treatment computer tasks & additional MRI scans. Note: The 1st phase of the study entered a R61 no cost extension at the end of the project period & due to limited funds, participants will no longer be receiving up to 4 scans. Participants who consent at UNC on or after 11/1/18 will receive only pre- and post treatment scans (2 scans total).

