## 1.3 SCHEDULE OF ACTIVITIES (SOA)

## TIMELINE OF STUDY ASSESSMENTS AND PROCEDURES:

Assessment/Procedure	Online/Phone Screen	Remote/In Person Screen (at Duke) - can be split in 1-2 visits (part remote/part in-person)**	Pre-Tx fMRI (at UNC)	Intervention therapy sessions at Duke) 	Wks 4, 8 & 12 (if applicable) 	fMRI (wk 8 & 12) 	Study Completion Visit-Part I (Duke)	Part II Post-Tx fMRI (UNC)
Online/Phone Screen Questionnaire	X							
Informed consent		X (via Duke REDCap econsent)	X (UNC specific consent)					
SHAPS	X	X	X	X	X	X	X	X
C-SSRS		X			X (post)		X (post)	
SCID5 relevant to inclusion /exclusion, NART		X						
SCID-5-RV		X						
[name] & Background info, CGI-S, CTQ		X						
R61 Phase: BDI-II, BAI, SF-36, PhenX depression & perceived stress, PCL-5, PSWQ, IDAS, TMS, SRS-2		X			X		X	
R33 Phase: BDI-II, BAI, SF-36, PhenX depression & perceived stress, PCL-5, PSWQ, TMS, MAPS, IDS-RS, BADS		X			X		X	
R33 Phase: WAI					X		X	
EEfRT, PRT		X			X		X	
Caffeine, Nicotine, Alcohol & sleep day of intake		X	X		X	X	X	X
Urine Pregnancy Test; PEERS (female only)			X (pre)			X (pre)		X (pre)
CGI-I, % homework tasks completed				X			X	
MID			X 			X		X
fMRI			X 			X		X
MRI checklist			X			X		X
Urine Drug Screen		X**						
Acceptability Questionnaire							X	

Between 8-15 weeks of therapy sessions (therapy will be either MBCT or BATA), in-person or remote during COVID-19 guidelines.

At visits week 4, 8 & 12 (if applicable), subjects will complete EEfRT & PRT computer tasks at the beginning of the visit followed by the therapy session or if during COVID-19 times, at a separate in-person visit from the remote therapy session. All paperwork done at therapy visits will be done in addition to procedures noted in this column. They will then complete the REDCap questionnaires at these key assessment time points (either in-person or done remotely by REDCap survey invitation). If the final therapy visit is before week 8, there will be three assessment points (pre-treatment, week 4, and at the last therapy visit). If the final therapy visit is between week 8 and week 12, there will be four assessment points (pre-treatment, week 4, week 8, and at the last therapy visit). If the final therapy visit is after week 12, there will be five assessment points, and post-treatment assessments will be administered either at the last therapy session or separately if therapy was remote. COVID-19

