Update: \*\*Please note that the conduct of the computer tasks with CSSRS at the in-person assessment visit, wks 4, 8, 12 and final visit are contingent upon the building availability and approval of in-person visits either at Duke or UNC. If not available and approved, the computer tasks with CSSRS will be omitted until the study team have the appropriate approvals to do the tasks at an in-person visit. These omissions (skipping the in-person visit) will not be considered protocol deviations since the omissions are necessary to be able to open the study and begin to collect the main primary outcomes of imaging and therapy.

This column is only for the first 60 subjects randomized as part of Phase I, R61. The R61 study will be entering a no-cost extension at the end of the current project period to allow for completion of data collection for this phase. Due to limited funds, the number of scans obtained is being reduced from up to 4 scans to two scans (pre- and post-treatment) for participants who are consented at UNC as of November 1.

MID practice is included & done first to determine reaction time

Includes mock scan and fMRI scan

\*\*While Duke is not open to in-person visits (COVID), this 2nd assessment visit that includes an additional CSSRS, alcohol, caffeine, sleep and 2 computer tasks, may be done at UNC. Urine drug screen would be skipped if done at UNC or there are not approvals at Duke for in-person visit and this won't be considered a protocol deviation.

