#### **Treatment (at Duke between 8-15 weeks)**

Patients will complete a course of BATA or MBCT. Subjects will be assigned a specific Duke study therapist and will continue with the same therapist through the 8-15 weeks of therapy. All therapy sessions will occur in Duke CBRTP located in the Civitan building ([name]) or via WebEx/Zoom Duke approved remote platforms. At the end of each therapy visit, the therapist will complete the Clinical Global Impairment scale in relation to improvement of symptoms (CGI-I) and the subject will complete the SHAPS. Starting at the second therapy session, the subject will be asked to give a % of how much of the homework tasks they had completed over the prior week since the last therapy session. The weekly therapy sessions will last around 1 hour, except for weeks 4, 8, 12, and the final therapy session (if not at week 8 or 12) as noted just below. All remote weekly therapy sessions will last around 1 hour.

Weeks 4, 8, and 12 (if applicable) : At these specific therapy visits, subjects will also be asked to complete the EEfRT and PRT computer tasks again. The tasks will be done and the subject will be asked about their caffeine, alcohol, nicotine & sleep habits over the past day in addition to completing SHAPS & % homework tasks completed over the past week (if not already completed during the therapy session). The subject may have their therapy session before or after these tasks & surveys or may be completed on a separate day during the week 4, 8, and 12. The C-SSRS will be administered after the computer tasks. They will then again be asked to complete most of the questionnaires they completed at the screening assessment visit (i.e. R61: the PSWQ, PCL-5, BDI-II, BAI, SF-36, IDAS, TMS, SRS-2, and PhenX measures of related to depressed mood and perceived stress, R33: the MAPS, IDS-RS measures related to anhedonia, BADS, WAI, PSWQ, PCL-5, BDI-II, BAI, SF-36, TMS, and PhenX measures of related to depressed mood and perceived stress). They will complete them directly in REDCap either in-person or by REDCap survey invitation. These visits will last from 2 to 2 ½ hours.

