Duke: At the final therapy visit (anytime between 8-15 weeks as determined by Duke/UNC study team) or separately, the subject will be asked to redo the computer tasks (EEfRT and PRT), complete the SHAPS & % homework tasks 1 last time and then again be asked to complete most of the online questionnaires they completed at the screening assessment visit ((i.e. R61: the PSWQ, PCL-5, BDI-II, BAI, IDAS, SF-36, TMS, SRS-2, PhenX measures of related to depressed mood and perceived stress, R33: the MAPS, IDS-RS measures related to anhedonia, BADS, WAI, PSWQ, PCL-5, BDI-II, BAI, SF-36, TMS, and PhenX measures of related to depressed mood and perceived stress). They will complete them directly in REDCap. Next, the C-SSRS will be done and the subject will be asked a series of questions about feasibility and acceptability of procedures (exit interview), and will be offered referrals for other mental health services as needed. Finally, they will be scheduled for their final fMRI brain scan at UNC. Note: Especially during COVID-19, the final computer tasks, CSSRS, exit interview, and caffeine/alcohol questions may be done at UNC and survey invitation sent out for the REDCap questionnaires. **\*\*Please note that the conduct of the computer tasks with CSSRS at the in-person final visit are contingent upon the building/room availability and approval of in-person visits either at Duke or UNC. If not available and approved, the computer tasks with CSSRS will be omitted until the study team have the appropriate approvals to do the tasks at an in-person visit. These omissions (skipping the in-person visit) will not be considered protocol deviations since the omissions are necessary to be able to open the study and begin to collect the main primary outcomes of imaging and therapy. If omitted, the participant will be emailed the REDCap survey invitation to complete only the self-report with exit interview, as applicable.**

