#### 10.1.10 PROTOCOL DEVIATIONS

A protocol deviation is any noncompliance with the clinical trial protocol, International Conference on Harmonisation Good Clinical Practice (ICH GCP), or Manual of Procedures (MOP) requirements. The noncompliance may be either on the part of the participant, the investigator, or the study site staff. As a result of deviations, corrective actions are to be developed by the site and implemented promptly.

Protocol violations that could represent serious or continuing noncompliance will be brought to the attention of the PI as soon as possible and not longer than 24 hrs. These violations will be reported to

the Duke University Medical Center Institutional Review Board using the appropriate documentation within 5 days of notification of the PIs. If these events are determined to be serious or continuing noncompliance by the Duke IRB, they will then be reported to the overall sponsor, NIMH, within 10 business days and entered on the study log. They will be reported to the DSMB < 4 weeks.

Protocol deviations around study visit windows, skipped questions on self-report measures, missed therapy sessions, etc. will not be reported to the Duke IRB. Other protocol deviations will be reported to the PIs upon discovery and will then be reported to the Duke IRB within 2 weeks. These deviations will in turn be reported to NIMH annually within the study progress report and reported to the DSMB per the DSMB designated meeting schedule. ***COVID-19 Update: \*\*Please note that the conduct of the computer tasks with CSSRS at the in-person assessment visit, wks 4, 8, 12 and final visit and the urine drug screen are contingent upon the building availability and approval of in-person visits either at Duke or UNC. If not available and approved, the computer tasks with CSSRS and urine drug screen will be omitted until the study team have the appropriate approvals to do the tasks at an in-person visit. If omitted (skipping the in-person visit), it will not be considered a protocol deviation since the omissions are necessary to be able to open the study and begin to collect the main primary outcomes of imaging and therapy.***

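### When in-person visits are not approved, the on-treatment C-SSRS is dropped together with the computer tasks while therapy can go on remotely, and no remote C-SSRS replaces it

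*Combined protocol and SAP*

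**What the plan says.** Section 4.2 (eligibility and diagnostic measures, item 1) and the Schedule of Activities in Section 1.3 place the C-SSRS at screening, at weeks 4, 8 and 12, and at the final visit. The treatment part of Section 4.2 fixes its position: "The C-SSRS will be administered after the computer tasks".

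The COVID-19 rule makes that visit depend on building availability and approval at Duke or UNC. Without approval, "the computer tasks with CSSRS will be omitted until the study team have the appropriate approvals to do the tasks at an in-person visit". The notes to Section 1.3 say the same ("If not available and approved, the computer tasks with CSSRS will be omitted until the study team have the appropriate approvals"), as do the final-visit text of Section 4.2 and Section 10.1.10 ("the computer tasks with CSSRS and urine drug screen will be omitted until the study team have the appropriate approvals to do the tasks"). All four places add that the omission is not a protocol deviation.

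Other parts of the study have a remote route. Section 1.3 footnote 1 and the treatment part of Section 4.2 allow remote therapy. For the questionnaires, footnote 2 says: "They will then complete the REDCap questionnaires at these key assessment time points (either in-person or done remotely by REDCap survey invitation". For a final visit that cannot be held in person, Section 4.2 says: "If omitted, the participant will be emailed the REDCap survey invitation to complete only the self-report with exit interview, as applicable". The C-SSRS is not in that list.

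**The concern.** The stated reason for the omissions is that the study could not otherwise open. That explains dropping laboratory tasks and a urine screen. It does not explain dropping an interview that the protocol already accepts remotely: under Section 5.2, criterion 6, if the in-person screening visit is omitted, the C-SSRS from the remote first assessment decides eligibility. A remote C-SSRS is good enough to admit a participant but is not used to monitor the same participant in treatment.

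The population makes this relevant. Section 2.3.3 expects some participants to have clinically significant depression and some not to improve. Section 6.3 allows up to 40% with a current depressive episode. Sections 5.2 and 6.5 keep antidepressants, mood stabilizers and antipsychotics out of the study. Section 2.3.3 says neither therapy has enough evidence to be the sole treatment for suicidal behavior, and so commits to excluding actively suicidal people for the whole trial. The C-SSRS is the scheduled, structured means of keeping that commitment. The immediate alert to the PI in Section 2.3.1 is tied to its items 4 and 5 and cannot fire if the scale is not given.

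Because the omission is not a deviation, it also escapes the deviation reporting to NIMH and the DSMB in Section 10.1.10.

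**Working it through.** The plan gives no figure to reproduce. The check has three parts.

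**1. What continues remotely when in-person visits are not approved**

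| Element | Remote route? | Where |
|---|---|---|
| Therapy sessions, with weekly CGI-I | Yes, by video | 1.3 footnote 1; 4.2 treatment |
| Self-report questionnaires | Yes, by REDCap invitation | 1.3 footnote 2; 4.2 |
| Exit interview | Yes | 4.2 final visit |
| C-SSRS at screening | Yes | 5.2, criterion 6 |
| C-SSRS at weeks 4, 8, 12, final | None described; omitted | 1.3 notes; 4.2; 10.1.10 |

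Remote therapy alone does not remove the C-SSRS. Footnote 2 provides for the tasks to be done "if during COVID-19 times, at a separate in-person visit from the remote therapy session". The gap opens only while approval for that visit is absent.

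**2. Number of scheduled assessments affected**

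Inputs: the C-SSRS follows the task time points, and the final visit coincides with week 8 or week 12 if therapy ends there (Section 4.2). The count covers participants who complete 8 to 15 weeks and includes the final visit.

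- Therapy ends at week 8: weeks 4, 8 = 2
- Ends in weeks 9-11: weeks 4, 8, final = 3
- Ends at week 12: weeks 4, 8, 12 = 3
- Ends in weeks 13-15: weeks 4, 8, 12, final = 4

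If the rule is in force throughout, each count becomes 0. If the final C-SSRS can still be done in person at UNC, which Section 4.2 permits, each becomes 1.

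Without the final visit, the counts before it are 2 - 1 = 1, 3 - 1 = 2, 3 - 1 = 2 and 4 - 1 = 3. All become 0 under the rule, with or without the UNC route.

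If the rule bites at one time point only, for example week 8, the interval between scheduled assessments is 12 - 4 = 8 weeks instead of 4.

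**3. What remains in force**

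- Weekly therapist contact with a CGI-I rating (4.2)
- Four-weekly depression, anxiety and trauma scales, with removal on a 10% rise (2.3.3)
- Immediate risk assessment if intent is reported to staff or on a symptom instrument (2.3.3)
- A health inquiry at study visits (8.1.4)
- Weekly supervision of therapists (8.1.6)

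None of these is a scheduled structured suicidality interview. The SCID, the other tool named in Section 2.3.1 for suicidality, is scheduled at screening only.

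**The case against.** The rule is disclosed, conditional and reasoned. It lasts only until approval is obtained. Amendments need IRB approval, and the DSMB's remit includes changes to risk management (Section 9.2.1). Detection does not rest on the C-SSRS alone: the risk-assessment trigger in Section 2.3.3 works without it, the questionnaires still go out at the same time points, and LCSW- or PhD-level clinicians see participants weekly, more often than the C-SSRS is given. Entry already excludes C-SSRS items 4 or 5 in the past month and an attempt within 6 months. Section 6.1.2 already lets some assessments go missing in ordinary operation, so a gap of about 8 weeks is not unique to this rule. Anyone with a post-treatment scan attends UNC in person and could have the final C-SSRS there. Nothing in the documents shows how often the rule was applied during treatment. Endpoints, power and analysis are untouched.

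Most of this stands and bears on weight. The remaining safeguards are substantial, and exposure to the rule is unknown. A fall to 0 is the extreme case, and the single-omission figure describes a participant with one omission, not a minimum across the trial.

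It does not close the gap. The remaining triggers depend on the participant volunteering intent or on instruments built for other purposes. An assessment missed because a participant did not attend differs from one the protocol tells staff not to give to a participant who is attending by video. The UNC route covers only the final visit, and enrolment into UNC procedures ended with the June 2022 amendment.

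**Conclusion.** The concern holds. Followed as written, the rule removes the only structured suicidality interview scheduled during treatment, for as long as in-person visits are unapproved, without a remote substitute and without being recorded as a deviation. The size per participant runs from one longer interval (about 8 weeks instead of 4, if week 8 alone is lost) to the loss of all 2, 3 or 4 scheduled assessments.

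The upper figure assumes an 8-15 week completer, the rule in force throughout, and no final C-SSRS at UNC. Early dropouts, who are asked to attend UNC in person, are not counted. Neither are individual R33 task visits skipped under Section 7.3, which are logged as deviations. The trial-wide effect cannot be estimated from the documents.

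The commitment to exclude actively suicidal participants throughout the trial is weakened but not contradicted. This is a safety-procedure point that should be corrected; it does not affect the statistical inference.

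**What to change.** Schedule the C-SSRS independently of the computer tasks. Whenever the task visit is omitted or skipped, give it by phone or video at weeks 4, 8, 12 and the final visit, as the protocol already accepts at screening.

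Align the wording in the Section 1.3 notes, the three places in Section 4.2 (eligibility measures, assessment-point clarification, final visit), Section 7.3 and Section 10.1.10. Two drafting inconsistencies can be settled at the same time: the omission sentence in the assessment-point clarification names only the tasks and the urine screen, and Section 7.3 is silent on the C-SSRS when a task visit is skipped. The text should also say how staff confirm a remote participant's location if items 4 or 5 are endorsed, since some response steps in Sections 2.3.1 and 2.3.3 assume the participant is on site.

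The cost is one interview per affected time point, at most four per participant, by staff who already use the instrument, plus the protocol wording. The documents give no administration time for the C-SSRS; I assume it is short. No new instrument is needed.
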